[18] have evidence of or test positive for hepatitis B virus (HBV) at screening, defined as (1) testing positive for hepatitis B surface antigen OR (2) testing positive for anti-hepatitis B core antibody (HBcAb) AND positive for HBV DNA

Subjects whose results are HBcAb positive and HBV DNA negative may be enrolled in the study, according to investigator judgment. Subjects whose results are HBcAb positive and HBV DNA negative at screening will be monitored for HBV during the study as detailed in Section 8.4.7.1.

[19] have evidence of or test positive for human immunodeficiency virus at screening

[20] have symptomatic herpes zoster within 6 months prior to screening that constitutes a clinically significant risk to the subject (according to investigator judgment)

- [21] have active tuberculosis (TB) determined on the basis of a positive medical history, physical examination, or chest radiography (per local standard of care) or have exclusionary TB test results, which include either of the following:
- a positive tuberculin skin test (TST) result (defined as a skin induration >5 mm at 48 to 72 hours after the test date, regardless of Bacillus Calmette-Guérin vaccination history) or
 - a positive (or persistently indeterminate/invalid/borderline) interferon γ release test (eg, QuantiFERON[®]-TB Gold or T-Spot[®].TB)

The choice to perform either a TST or an interferon γ release test will be made by the investigator according to local licensing and standard of care. If the QuantiFERON-TB Gold is indeterminate or the T-Spot.TB is invalid or borderline, one retest is allowed according to investigator judgment. If the repeat test is also indeterminate, the subject will be excluded. The interferon γ release test can be used only in countries where it is licensed, and the use of this test is dependent on previous treatment(s).

Subjects with known latent TB should not undergo a TST or interferon γ release test and must have documentation of receiving at least 4 weeks of appropriate, ongoing latent TB therapy, according to local standard of care, prior to screening. Such patients must continue/complete appropriate latent TB therapy during the course of the study in order to remain eligible.

- [22] are at high risk of infection or have recent evidence of clinically significant infection, based on findings that include the following:
- fever of 100.5°F (38°C) or above at screening or baseline that is not due to the underlying autoimmune disease (eg, RA)

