8.4.2. Vital Signs

Blood pressure and heart rate will be measured as specified in the Schedule of Activities ([Appendix 2](#)) and as clinically indicated. These should be measured after at least 5 minutes of sitting.

Unscheduled orthostatic vital signs should be assessed, if possible, during any AE of dizziness or posture-induced symptoms. If the subject feels unable to stand, sitting or supine vital signs should be recorded.

Additional vital signs may be measured during each study visit if warranted, as determined by the investigator.

Body temperature will be measured as specified in the Schedule of Activities ([Appendix 2](#)) and as clinically indicated.

Any clinically significant findings that occur after the subject receives the first dose of study drug should be reported to Lilly or its designee as an AE via the eCRF.

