Appendix 2. Schedule of Activities

Tables presenting the Schedule of Activities for Part A and Part B are provided after the summary of study periods presented below.

Part A:

Screening Period (Visit 1, Weeks –4 to 0)

A screening period to assess subject eligibility will begin at Visit 1 and can last up to 28 days. Subjects will sign the ICF before any study assessments, examinations, or procedures are performed. Details regarding inclusion/exclusion criteria are in Sections 5.1 and 5.2. Refer to the Schedule of Activities table for details regarding screening procedures.

Dosing Period (Visits 2 to 5; Weeks 0 to 4; Study Days 1 to 29)

Subjects will be randomly assigned at baseline (Visit 2) in a 1:1:1:1 ratio to 1 of 4 arms: 3 experimental arms in which LY3337641 will be dosed orally at 5, 10, or 30 mg and 1 placebo comparator arm. Study drug will be administered qd in a blinded fashion from Week 0 through Week 4. Four clinic visits are planned during this period (Visits 2 to 5) at Weeks 0, 1, 2, and 4. At these visits, subjects will undergo safety evaluations, clinical assessments, PK samplings, and other laboratory assessments according to the Schedule of Activities table.

Safety Follow-Up Period (Visit 801, Week 6, Study Day 43)

All subjects will have a safety visit (Visit 801) at least 2 weeks after the final dose of study drug. For subjects who discontinue the study early, an additional safety visit is only required if the EDV occurs less than 2 weeks after the last dose of study drug.

Part B:

Screening Period (Visit 101, Weeks –4 to 0)

A screening period to assess subject eligibility will begin at Visit 101 and can last up to 28 days. Subjects will sign the ICF before any study assessments, examinations, or procedures are performed. Details regarding inclusion/exclusion criteria are in Sections 5.1 and 5.2. Refer to the Schedule of Activities table for details regarding screening procedures.

Dosing Period (Visits 102 to 106; Weeks 0 to 12; Study Days 1 to 85)

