Subjects will be randomly assigned at baseline (Visit 102) in a 1:1:1:1 ratio to 1 of 4 arms: 3 experimental arms in which LY3337641 will be dosed orally at 5, 10, or 30 mg and 1 placebo comparator arm. Study drug will be administered qd in a blinded fashion from Week 0 through Week 12. Five clinic visits are planned during this period (Visits 102 to 106) at Weeks 0, 2, 4, 8, and 12. At these visits, subjects will undergo safety evaluations, clinical assessments, PK samplings, and other laboratory assessments according to the Schedule of Activities table.

Safety Follow-Up Period (Visit 802, Week 14, Study Day 99)

All subjects will have a safety visit (Visit 802) at least 2 weeks after the final dose of study drug. For subjects who discontinue the study early, an additional safety visit is only required if the EDV occurs less than 2 weeks after the last dose of study drug.

Additional HBV DNA Monitoring (Visits 803 and 804, Study Days 169 to 253)

HBV DNA will be monitored every 3 months (for 6 months) after the last dose of study drug for those subjects who are HBcAb+ and HBV DNA negative (undetectable) at screening.

Schedule of Activities, Protocol I8K-MC-JPDA – Part A

Perform procedures as indicated.

	Screening	Baseline (Random- ization)	Dosing Period			Safety Follow-Up	Comments
	V1	V2	V3	V4	V5 & EDV	V801 ^a	
eCRF Visit Number (V)	V1	V2	V3	V4	V5 & EDV	V801 ^a	
Study Day (\pm day(s))	≤ 28 Days from V2	1	8 ± 3	15 ± 3	29 ± 3	43 +7	
Study Week		0	1	2	4	6	
Informed consent	X						Must be completed prior to performing any study-related procedures or tests.
Review and confirm inclusion/exclusion criteria	X	X					
Complete medical history, pre-existing conditions	X						
Complete physical exam	X						
Symptom-directed physical exam (as clinically indicated)		X	X	X	X	X	Symptom-directed physical examinations are not required at each visit but may be conducted at the investigator's discretion at any visit and any time a subject presents with complaints.
Adverse events	X	X	X	X	X	X	AEs will be graded as mild/moderate/severe except rash, which will use CTCAE grading.
Concomitant drugs	X	X	X	X	X	X	
Height	X						Subject should remove shoes.
Body weight	X	X			X		
Vital signs	X	X	X	X	X	X	Vital signs include heart rate and blood pressure.
Temperature	X						May be repeated as clinically indicated.
ECG	X						A local ECG will be collected at screening and may be repeated at the investigator's discretion at any visit.

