Abbreviations: ACPA = anti-citrullinated peptide antibodies; AEs = adverse events; BCG = Bacillus Calmette-Guérin; BTK = Bruton's tyrosine kinase; CCP = cyclic-citrullinated peptide; CTCAE = Common Terminology Criteria for Adverse Events; ECG = electrocardiogram; eCRF = electronic case report form; EDV = early discontinuation visit; FSH = follicle-stimulating hormone; HAQ-DI = Health Assessment Questionnaire–Disability Index; HBcAb = hepatitis B core antibody; HBsAb = hepatitis B surface antibody; HBV = hepatitis B virus; HCV = hepatitis C virus; HIV = human immunodeficiency virus; hsCRP = high-sensitivity C-reactive protein; Ig = immunoglobulin; LY = LY3337641; PA = posteroanterior; pBTK = phosphorylated BTK; RF = rheumatoid factor; TB = tuberculosis; TSH = thyroid-stimulating hormone; TST = tuberculin skin test; V = visit; VAS = visual analog scale.

^a For subjects who discontinue the study early, the safety visit will be at least 2 weeks after the final dose of study drug and is required only if the EDV occurs less than 2 weeks after the final dose.

Schedule of Activities, Protocol I8K-MC-JPDA – Part B

Perform procedures as indicated.

	Screening	Baseline (Randomi- zation)	Dosing Period				Safety Follow -Up	Additional HBV DNA Monitoring		Comments
			V101	V102	V103	V104		V105	V106 & EDV	
eCRF Visit Number (V)	V101	V102	V103	V104	V105	V106 & EDV	V802 ^a	V803 ^b	V804 ^b	
Study Day (±day(s))	≤28 Days from V2	1	15 ±2	29 ±2	57 ±3	85 ±3	99 +7	169 ±7	253 ±7	
Study Week		0	2	4	8	12	14	24	36	
Informed consent	X									Must be completed prior to performing any study related procedures or tests.
Review and confirm inclusion/exclusion criteria	X	X								
Complete medical history, pre-existing conditions	X									
Complete physical exam	X									
Symptom-directed physical exam (as clinically indicated)		X	X	X	X	X	X	X	X	Symptom-directed physical examinations are not required at each visit but may be conducted at the investigator's discretion at any visit and any time a subject presents with complaints.
Adverse events	X	X	X	X	X	X	X	X	X	AEs will be graded as mild/moderate/severe except rash, which will use CTCAE grading.
Concomitant drugs	X	X	X	X	X	X	X	X	X	
Height	X									Subject should remove shoes.
Body weight	X	X				X				
Vital signs	X	X	X	X	X	X	X	X	X	Vital signs include heart rate and blood pressure.
Temperature	X									May be repeated as clinically indicated.

Schedule of Activities, Protocol I8K-MC-JPDA – Part B

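### Exclusion [22] bars fever at screening or baseline, but neither Schedule of Activities marks a temperature at baseline, so the baseline check is left to investigator judgment

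*Protocol*

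**What the plan says.** Exclusion [22] (Protocol 5.2) covers subjects at high risk of infection or with recent evidence of a clinically significant one. Its first listed finding is a "fever of 100.5°F (38°C) or above at screening or baseline that is not due to the underlying autoimmune disease". This is a numeric limit tied to two visits.

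Protocol 8.4.2 sets the timing: "Body temperature will be measured as specified in the Schedule of Activities". The same sentence adds measurement when clinically indicated.

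In Appendix 2, the Temperature row is marked only at V1 (Part A) and only at V101 (Part B). The comment on that row is "May be repeated as clinically indicated". The vital signs row is marked at V2 and V102, but its comment reads "Vital signs include heart rate and blood pressure". The row "Review and confirm inclusion/exclusion criteria" is marked at both screening and baseline in each part. For Part B, "A screening period to assess subject eligibility will begin at Visit 101 and can last up to 28 days"; Part A has the same limit.

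**The concern.** The site has to confirm at V2 or V102 that no exclusion applies, and [22] names that visit. Yet the schedule does not ask for the measurement that [22] needs on that day. A site that follows the schedule exactly can confirm eligibility, randomize and give the first dose without a temperature.

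Measuring when clinically indicated mostly produces a reading when illness is already suspected. A numeric exclusion is normally meant to apply to everyone, so the subject most likely to be missed is one with fever and few complaints.

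This is a safety eligibility check in the first trial of this BTK inhibitor in RA. Background methotrexate or leflunomide, and oral prednisone up to 10 mg/day, are permitted. An infection that was present but unrecognized at baseline, and then recorded with an onset after the first dose, would meet the treatment-emergent definition in SAP 6.4.2 and enter the infection summaries in SAP 6.4.5.6.

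**Working it through.** **Schedule against criterion.** This part is a comparison of the provisions, not a calculation.

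| Item | Screening (V1 / V101) | Baseline (V2 / V102) |
|---|---|---|
| Fever limit in [22] applies | Yes | Yes |
| Eligibility reviewed and confirmed | Yes | Yes |
| Temperature marked in the schedule | Yes | No |
| Vital signs marked (heart rate, blood pressure) | Yes | Yes |
| Physical examination | Complete | Symptom-directed, at the investigator's discretion |

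The fever limit is the only item that applies at baseline without its own measurement being scheduled there. Neither the vital signs nor the physical examination fills the gap, because the first excludes temperature and the second is optional.

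Pregnancy testing shows the opposite pattern. Inclusion [2] asks for a negative test at screening only, yet both schedules add a urine test at baseline for women of childbearing potential. For fever, the criterion names baseline and the schedule adds nothing.

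**Extent.** Planned enrollment is 32 (Part A) + 244 (Part B) = 276 subjects, and none has a scheduled baseline temperature. The longest interval from the scheduled reading to baseline is the 28-day screening period. The documents give no rate of fever or intercurrent infection, so the number of subjects affected cannot be calculated.

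**Units (separate point).** The criterion gives 100.5°F and 38°C as one limit.

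- Fahrenheit to Celsius: (100.5 − 32) × 5/9 = 38.06°C. This rounds to 38°C at the whole degree, which reproduces the pair as printed, but to 38.1°C at one decimal.
- Celsius to Fahrenheit: 38 × 9/5 + 32 = 100.4°F.
- Difference: 100.5 − 100.4 = 0.1°F, or about 0.06°C.
- Neighboring readings: 37.9°C = 100.2°F is below both limits; 38.1°C = 100.6°F is above both.

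At a resolution of 0.1 degree, only a reading of 38.0°C (100.4°F) is classified differently. It is exclusionary by the Celsius figure and not by the Fahrenheit figure. This applies equally at screening, so it is not a cause of the baseline gap.

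**The case against.** The strongest reply is that the plan already lets a site do what [22] asks. Eligibility must be confirmed at V2 or V102, temperature may be repeated, and a criterion that names a baseline temperature is itself a reason to take one. That stands. A reader might infer that the baseline half of [22] cannot be applied at all; the documents do not support this. They support only that a baseline reading is not guaranteed.

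Other safeguards are also in place. Fever is one of several findings under [22], exclusion [30] covers any clinically significant condition or finding, and adverse events and concomitant drugs are recorded at baseline. So [22] is not confined to screening. These routes rely on judgment or on reported symptoms, however, and do not replace a measured limit.

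Three further inferences should be resisted:

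- That a breach would go undetected because SAP Table JPDA.6.1 has no row for [22]. The table also has none for [20], [21], [23] to [31] or [33] to [36], and the protocol provides for source-document checks (10.2) and for inadvertently enrolled subjects (7.1.3).
- That infections would certainly be misclassified as treatment-emergent. Events with onset before the first dose count as baseline; misclassification requires an infection that was unrecognized at the visit and later dated after dosing.
- That most subjects will be on background immunosuppressants. The protocol permits these drugs but does not say how often they will be used.

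Finally, the conflict could be removed from the other side, by changing the visits that [22] names. That choice is the sponsor's. What cannot stay is a criterion and a schedule that disagree.

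**Conclusion.** The inconsistency is real and present in both parts: [22] applies at two visits, and temperature is scheduled at one. As a result the baseline half of the criterion is applied at the investigator's discretion and not systematically, up to 28 days after the only scheduled reading. The gap covers every planned subject by design, but 276 is the number without a scheduled reading, not an estimate of subjects wrongly enrolled.

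This rests on reading the Temperature row and its comment as the complete instruction to sites, as 8.4.2 indicates. A site manual that required a baseline temperature would close the gap in practice, but neither document mentions one.

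The matter is one of eligibility and subject safety. It does not touch the ACR20 analysis or the sample size. It is worth correcting because the correction is cheap. The unit discrepancy is an editorial matter of 0.1°F.

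**What to change.** Reconcile exclusion [22] with the Temperature rows in both Schedules of Activities, so that every visit the criterion names has a scheduled reading before randomization and first dose. Marking Temperature at V2 and V102 would do this. In the same amendment, make the two limits in [22] the same temperature or state which unit governs; the sponsor decides the limit.

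The cost is one thermometer reading at a visit that already takes pulse and blood pressure, plus a change of wording. No visit is added. The downside is an occasional subject found febrile at baseline who has to rescreen. Protocol 5.3 allows this once, with written sponsor approval and new consent, if the fever has resolved without intravenous antibiotics or hospitalization and the investigator judges that it poses no risk to participation.

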5.3. Screen Failures

Individuals who do not meet the criteria for participation in this study (screen failure) may be rescreened ONE time in selected situations upon written approval from the sponsor (eg, if they failed to meet minimum disease activity criteria defined in Inclusion Criterion [7] at initial screening, required more time for appropriate drug washout periods, tested positive for latent TB and subsequently completed at least 4 weeks of appropriate prophylactic treatment, or had a fever (Exclusion Criterion [22]) that resolved, did not require IV antibiotics or hospitalization, and did not pose a risk to the subject for participation in the study, according to investigator judgment). Subjects who failed screening in Part A may be rescreened for either Part A or Part B; however, only ONE rescreen is permitted regardless of which part the subject is rescreening for.

Subjects who fail screening because of administrative reasons (eg, fall out of the screening window because of scheduling reasons) may be rescreened ONE time (in addition to the above) upon written approval from the sponsor.

If rescreening is performed, the individual must sign a new informed consent form (ICF) for each rescreening and will be assigned a new identification number. Subjects in rescreening who have previously completed screening chest radiography and/or TB tests according to the protocol do not need to repeat these procedures if they were performed within 90 days before their rescreening date of consent but may do so at the discretion of the investigator.

5.4. Lifestyle and/or Dietary Requirements

Strenuous exercise should be avoided for at least 24 hours before study visits.

Subjects should continue their usual dietary intake during the study.

6. Treatment

6.1. Treatments Administered

This study involves a comparison of each LY3337641 dosing regimen (5, 10, and 30 mg administered orally qd) with placebo. The study drug is supplied as tablets containing 5 and 20 mg of LY3337641 with matching placebo tablets. A single dose in Part A will include 4 tablets in various combinations depending on the assigned regimen. [Table JPDA.3](#) shows the combinations of tablets used for the 4 dosing regimens. A single dose in Part B will include 4 tablets in various combinations depending on the assigned regimen. [Table JPDA.4](#) shows the combinations of tablets used for the 4 dosing regimens. More information on the tablets and blinded regimens can be found in [Section 6.4](#).

Table JPDA.3. Dosing Regimens – Part A

Regimen ^a	20-mg Tablets	5-mg Tablets
LY 30 mg	1 × 20-mg LY tablet 1 × 20-mg matching placebo tablet	2 × 5-mg LY tablets
LY 10 mg	2 × 20-mg matching placebo tablets	2 × 5-mg LY tablets
LY 5 mg	2 × 20-mg matching placebo tablets	1 × 5-mg LY tablet plus 1 × 5-mg matching placebo tablet
Placebo Comparator	2 × 20-mg matching placebo tablets	2 × 5-mg matching placebo tablets

Abbreviation: LY = LY3337641.

^a Each dose consists of 4 tablets taken orally once daily (qd). The 5- and 20-mg placebo tablets match the respective 5- and 20-mg LY tablets.

Table JPDA.4. Dosing Regimens – Part B

Regimen ^a	20-mg Tablets	5-mg Tablets
LY 30 mg	1 × 20-mg LY tablet	2 × 5-mg LY tablets 1 × 5-mg matching placebo tablet
LY 10 mg	1 × 20-mg matching placebo tablet	2 × 5-mg LY tablets 1 × 5-mg matching placebo tablet
LY 5 mg	1 × 20-mg matching placebo tablet	1 × 5-mg LY tablet 2 × 5-mg matching placebo tablet
Placebo Comparator	1 × 20-mg matching placebo tablet	3 × 5-mg matching placebo tablets

Abbreviation: LY = LY3337641.

^a Each dose consists of 4 tablets taken orally once daily (qd). The 5- and 20-mg placebo tablets match the respective 5- and 20-mg LY tablets. Four (4) tablets are required to provide for intermediate doses in the event of dose modification as defined in [Section 6.6](#).

The investigator or his/her designee is responsible for the following:

- explaining the correct use of the study drug to the subject
- verifying that instructions are followed properly
- maintaining accurate records of study drug dispensing and collection

- returning all unused medication to Lilly, or its designee, at the end of the study, unless the sponsor and sites have agreed that all unused medication is to be destroyed by the site, as allowed by local law

6.2. Method of Treatment Assignment

For Part A, subjects who meet all criteria for enrollment will be randomly assigned in a 1:1:1:1 ratio to 1 of the 4 study arms at Visit 2 in a double-blind fashion. For Part B, subjects who meet all criteria for enrollment will be randomly assigned in a 1:1:1:1 ratio to 1 of the 4 study arms at Visit 102 in a double-blind fashion. Assignment to treatment groups will be determined by a computer-generated random sequence using an interactive web-response system (IWRS). The IWRS will be used to assign packages containing double-blind study drug to each subject. Site personnel will confirm that they have located the correct packages by entering a confirmation number found on the package label into the IWRS.

To achieve between-group comparability in Part B, randomization will be stratified by biologic DMARD experience (yes/no), region (Japan vs non-Japan), and disease severity (Disease Activity Score modified to include the 28 diarthrodial joint count [DAS28]-hsCRP ≤ 5.1 vs >5.1). The screening value for hsCRP will be used to calculate DAS28-hsCRP (Section 8.1.2.2) for randomization.

6.2.1. Selection and Timing of Doses

Subjects will be randomly assigned to the dosing regimens as described in Section 6.2, and the assigned study drug will be administered as described in Section 6.1. Subjects will be instructed to take doses at approximately the same time each day. Study drug may be taken with or without food. The time of dose administration before a scheduled PK sampling should be recorded by the site at the clinic visit.

